7.4 Report to family

The family will receive a report of the neurodevelopmental assessment at 2 and 5 years. If any significant problems are identified the family will be notified and the child's paediatrician or family doctor. The child's paediatrician or family doctor may offer relevant referral to appropriate medical or allied health professionals.

8. STATISTICAL CONSIDERATIONS

8.1 Analysis of primary outcome

Since this an equivalence study, the primary outcome will be analysed on a perprotocol analysis basis to ensure a conservative estimate in the direction of nonequivalence. The means will be adjusted for gestational age at birth. The adjusted mean difference in Full Scale IQ Score between arms will be presented with a 2-sided 95% confidence interval. Equivalence will be accepted if the confidence interval of the difference in means lies within -5 and +5 points.

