3.5.6.3 Details of protocol violations

Details of any protocol violation including need for opioids or nitrous oxide Details of management for failed block

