4.5 Subject withdrawal criteria

4.5.1 Failed regional block with general anaesthesia

If the child is having a general anaesthetic (with sevoflurane) and the local anaesthesia block is inadequate (persistent tachycardia or hypertension), then opioids or nitrous oxide may be given at the discretion of the anaesthetist. Post-operative recovery and apnoea data will still be collected, as will neurodevelopmental data. These children will also be followed up in hospital and with a phone call 5 days postanaesthesia as per study protocol. Subjects will not be replaced.

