4.5.3 Cancellation of surgery

If the surgery is cancelled after randomisation and not rescheduled, or cancelled and rescheduled greater than 48 hours after randomisation, then the reason for cancellation must be noted and the case is treated as a protocol violation. The child is not replaced. If the child has a hernia repair after 48 hours, the child should receive anaesthesia at the anaesthetist's discretion. Anaesthetic, apnoea and recovery data may be collected if possible. Note that as per other violations, the child should receive two and five year developmental assessment as per protocol. If the child receives surgery for hernia repair 48 hours or more after initial randomisation then they cannot be randomised again in the trial for that later surgery.

Note surgery may be *delayed for up to 48 hours* and the child retains their position in the study with same study group and study number (provided they continue to meet inclusion criteria).

If before anaesthesia and after randomisation a decision is made by surgeon or anaesthetist that the child is no longer suitable for the study for whatever reason (apart from cancelled surgery or withdrawn consent) and the child does not receive their allocated anaesthesia protocol, then the case should be treated as a protocol violation and data collected as possible. The child should receive the same post-anaesthesia apnoea data collection and developmental follow-up as per protocol. Note that if treating staff consider that it is in the child's best interests they always have the opportunity to not follow the protocol, but only the parents can withdraw the child completely from the trial.

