5.7 Triggers to abandon awake regional and administer general anaesthesia

If there is a failed awake regional on clinical assessment then the infant is given a general anaesthetic with sevoflurane alone and continues in the study. In this situation the airway management is at the discretion of the anaesthetist. Regional failure may be due to movement impeding surgery or a vigorous crying child that cannot be comforted.

Note: If there is total failure of a spinal then the spinal may be attempted again with another 1mg/kg bupivacaine or levobupivacaine. Total failure is defined as follows: after 5 minutes the infant continuing to vigorously spontaneously move both their legs with no evidence of motor block and withdrawing both their legs after gentle pinch to either thigh. Any suggestion of only partial failure and the child should not receive another spinal attempt. Total dose of bupivacaine or levobupivacaine for entire case may not exceed 2.5 mg/kg.

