8.3 Justification of numbers

The WPPSI-III full scale IQ score is a standardised score with a mean of 100 and standard deviation of 15. Cohort studies of ex-preterm babies at 5 years of age commonly show a mean of 95 and standard deviation of 15, while term babies have a mean of approximately 105 and a standard deviation of 15. A difference of 5 points (1/3 of a standard deviation) will be taken as the largest difference that would be acceptable to demonstrate equivalence.

The sample size is calculated using the two one-sided equivalence tests method (ref: Schuirmann, D.J.) with a one-sided alpha of 0.025, applied to the null hypothesis that the two methods of anaesthesia are not equivalent, and power of 90% under the alternative hypothesis that the true mean difference is one standardised score point. Restated, we require 90% probability that the 95% confidence interval for the difference in means, adjusted for gestational age at birth, will exclude a difference of 5 or more (i.e. the 95% CI will lie within the range -5 to +5), if the true difference is no more than one point. The trial then needs 598 infants in total. Enrolling 660 will allow for an average of 10% loss to follow-up.

Adjusting the analysis for gestational age at birth, according to the three categories used in the stratified randomization, will ensure that the common standard deviation assumption is protected from the differences in WPPSI-III full scale IQ mean scores between the gestational age groups. Simulations have been performed to confirm these calculations.

Reference

Schuirmann, D.J. A comparison of the two one-sided tests procedure and the power approach for assessing the equivalence of average bioavailability. Journal of Pharmacokinetics and Biopharmaceutics 15(1987) pp. 657-680

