9. DATA MANAGEMENT

The Clinical Epidemiology and Biostatistics Unit (CEBU) at the Royal Children's Hospital in Melbourne will be the Data Coordinating Centre for the study, and will be receiving original CRFs from central locations in the USA and the UK and entering these CRFS into a database. Boston will receive a blank duplicate of the database used in CEBU and will double enter the data using photocopied CRFs. At regular intervals the databases will be compared to identify entry errors. The following process will ensure that CEBU receives all originals and Boston receives all photocopies of CRFs.

CRFs from Australian sites will be photocopied and the originals sent to Melbourne; CRFs from European sites will be photocopied and the originals sent to Glasgow; CRFs from USA sites will photocopied and the originals sent to Boston. From Glasgow the original deidentified CRFs will be sent to Melbourne and a photocopy sent to Boston. From Boston the original deidentified CRFs will be sent to Melbourne and a copy kept in Boston. From Melbourne a deidentified photocopy of the CRFs will be sent to Boston and the original kept in Melbourne.

Melbourne, Boston and Glasgow will be responsible for identifying and chasing missing data in their region. Melbourne, Boston and Glasgow will keep all identifying data and be responsible for arranging follow-up within their region.

All chief investigators will have access to all data, but blinded to allocation.

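### Equivalence is decided on a per-protocol analysis alone; this limits dilution but does not ensure a conservative result, and no as-randomised analysis stands beside it

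*Protocol*

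**What the plan says.** Protocol section 8.1 fixes both the population and its justification: "the primary outcome will be analysed on a perprotocol analysis basis to ensure a conservative estimate in the direction of nonequivalence". The decision rule follows: "Equivalence will be accepted if the confidence interval of the difference in means lies within -5 and +5 points". Section 8.2.1 applies per-protocol and the same limits to the Bayley III cognitive score at 2 years. The protocol names no analysis of children as randomised.

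Two provisions determine who may leave a per-protocol set. Under section 5.7, "If there is a failed awake regional on clinical assessment then the infant is given a general anaesthetic with sevoflurane alone", and the infant stays in the study; the triggers are movement that impedes surgery or crying that cannot be settled. Under section 4.5.3, the allocated protocol may be set aside before anaesthesia if "a decision is made by surgeon or anaesthetist that the child is no longer suitable for the study for whatever reason". Such a case is a protocol violation, but developmental follow-up continues. Section 3.3 states that the anaesthetist knows the allocation.

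**The concern.** A per-protocol estimate is protected against dilution, but it is conservative only if the infants removed have the same expected IQ as those kept. That is doubtful here. Conversion to general anaesthesia exists only in the regional arm, and its triggers partly reflect the infant's own behaviour. The general anaesthesia arm loses no matching group, so the comparison is no longer fully randomised.

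At stake is the primary conclusion, judged against a margin of 5 IQ points. A shift of half a point to one point matters at that scale. Section 1.4.2 of the protocol justifies a randomised trial by the confounding in cohort data; a decision that rests only on a post-randomisation subset lets part of that problem back in.

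**Working it through.** **Inputs from the protocol.** Margin 5, SD 15, design true difference 1, power 90%, 598 evaluable, 660 enrolled, and two one-sided tests "with a one-sided alpha of 0.025" (all section 8.3). Awake blocks are restricted to operators with more than 90% success (section 5.2.3), which makes f = 10% a reasonable working value. Equal allocation is assumed, since no ratio is stated.

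**Assumptions.** Only converted regional infants are excluded. Converted infants carry the full effect of general anaesthesia. The gap d runs from 0 to 10 points; the documents give no value.

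**The plan's own figure.** Two one-sided tests with the t distribution need 299 per arm, 598 in total (power 0.9007). The stated number is reproduced. After 10% loss, 660 × 0.9 = 594, or 297 per arm.

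**Formula.** P(equivalence) = Φ((5 − δ)/se − 1.96) + Φ((5 + δ)/se − 1.96) − 1, where δ is the expected value of the estimate and se = 15 × √(1/n₁ + 1/n₂).

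- Per-protocol, f = 10%: 297 against 267, se = 1.265, δ = true difference ± f × d.
- As-randomised: 297 against 297, se = 1.231, δ = true difference × (1 − f).

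**Worked case.** True difference 5, d = 5, bias toward zero: δ = 5 − 0.5 = 4.5. The first term is Φ(0.5/1.265 − 1.96) = Φ(−1.565) = 0.059, and the other two terms cancel to within rounding.

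| d | bias f × d | False equivalence, true difference 5, bias toward zero | Power, true difference 1, bias away from zero |
|---|---|---|---|
| 0 | 0 | 2.5% | 88% |
| 2 | 0.2 | 3.6% | 85% |
| 5 | 0.5 | 5.9% | 79% |
| 10 | 1.0 | 12.1% | 66% |

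**Intention-to-treat alone.** Dilution gives δ = 5 × 0.9 = 4.5, and Φ(0.5/1.231 − 1.96) = Φ(−1.554) = 6.0%. The two analyses lose the same amount when f × d = f × 5, that is, at d = 5.

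**Requiring both.** The two estimates share most of their data. Their variances are 225 × (1/297 + 1/267) = 1.600 and 225 × 2/297 = 1.515. The covariance is also 1.515, so the correlation is √(1.515/1.600) = 0.97. Under a bivariate normal with these values and f = 10%:

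- False equivalence at a true difference of 5, bias toward zero: d = 5, from 5.9% to about 4.9%; d = 10, from 12.1% to 5.9%.
- Power at a true difference of 1, no bias or bias away from zero: a loss of 0.2 to 0.6 points against per-protocol alone.
- Power at a true difference of 1, bias toward zero: a loss of 1.4 points at d = 2, 3.3 at d = 5 and 6.2 at d = 10 (95.4% to 89.2%; per-protocol power is itself inflated there).

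**The case against.** The strongest reply is that the protocol's choice is the better single analysis. Dilution under intention-to-treat follows directly from conversion, whereas per-protocol bias needs a link between block failure and IQ. With no link, per-protocol keeps false equivalence at 2.5% against 6.0%. It matches intention-to-treat only when d reaches 5 points in the unfavourable direction. Gestational age, the confounder that the protocol considers most important, is already in the model. Direction matters too: if infants with failed blocks score lower, excluding them widens an apparent deficit under general anaesthesia, which is conservative against missing harm. All of this stands. It shows that per-protocol is often conservative, not that conservatism is ensured.

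A statistical analysis plan may also add an intention-to-treat analysis and define the per-protocol set, so the absence of those details is not the complaint. The protocol itself, however, names the deciding population and gives a reason for it, and that reason claims too much.

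Some stronger readings are tempting but unsupported:

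- That failed blocks occur only in the regional arm. Section 4.5.1 deals with failed blocks under general anaesthesia, and cancellations can affect either arm. Only conversion is one-sided.
- That every child is followed to 5 years. Section 4.5.2 allows withdrawal and section 8.3 expects 10% loss.
- That the opioid and nitrous oxide provisions ("opioids or nitrous oxide may be given at the discretion of the anaesthetist" in 4.5.1, "any protocol violation including need for opioids or nitrous oxide" in 3.5.6.3) undermine the analysis set. A discretionary departure that is logged as a violation fits section 4.5.3, and its per-protocol status can be left to the analysis plan.
- That chief investigators could shape exclusions knowing the arm. Section 9 says "All chief investigators will have access to all data, but blinded to allocation", and nothing says that they see unmasked anaesthesia forms or decide membership.

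**Conclusion.** The point holds in limited form. Per-protocol is a defensible component of the decision, but it is not guaranteed to be conservative and should not decide equivalence alone. With 10% of the regional arm excluded, the risk of false equivalence at the margin runs from the nominal 2.5% to 12.1% as d goes from 0 to 10 points with bias toward zero. With bias away from zero, power at a true difference of 1 runs from 88% down to 66%. For small gaps the effect is modest: at d = 2 the figures are 3.6% and 85%.

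These results rest on d, which the documents do not give, on exclusions confined to converted infants, and on 297 per arm with SD 15. A reader might infer that per-protocol is the wrong choice or is anti-conservative. The documents do not support that: neither the direction nor the size of the bias is known, and intention-to-treat alone carries 6.0% false equivalence through dilution.

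**What to change.** - In section 8.1, replace the assurance of a conservative estimate with a statement that per-protocol limits dilution from conversion.
- Add an as-randomised analysis of all assessed children, with the same gestation-adjusted model, for the primary outcome and the Bayley III cognitive score.
- Accept equivalence only if the 95% confidence intervals from both analyses lie within -5 to +5. No alpha adjustment is needed, because both must succeed.
- Settle per-protocol membership by one rule for both arms before outcomes are seen.

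The cost is protocol wording and one further run of the same model, since protocol violations already receive the 2- and 5-year assessments. At a true difference of 1 and f = 10%, power falls by a few tenths of a point to about 3 points for gaps up to 5, and by about 6 points at a gap of 10 with bias toward zero. The double requirement reduces the selection bias problem but does not remove it.

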Due to the difficulties with cohort data, the best way to provide convincing evidence for the safety of volatile anaesthesia is with a prospective randomised trial. Fortuitously, in many sites, anaesthesia is provided to infants undergoing inguinal hernia repair via one of two methods – general anaesthesia (GA) or regional anaesthesia (RA). RA can be with spinal or caudal anaesthesia or a combination of both. RA can be provided without exposure to any of the agents purported to be associated with neuro-toxicity. Inguinal hernia repair is one of the most common procedures to be performed in infancy and provides a large population of infants having similar surgery. The reasons for choosing RA or GA may depend on the age of the child, the experience of the surgeon or anaesthetist, and the perceived risk of apnoea. As outlined below the risks of apnoea after modern anaesthesia are not clearly defined. The presence of equipoise in choice of anaesthesia for a single, relatively common procedure provides an ideal setting for a prospective randomised trial. The most important potentially confounding variable is the influence of prematurity on developmental outcome and choice of anaesthesia. This potentially confounding variable makes stratified randomisation and a subsequent stratified analysis essential.

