3. STUDY DESIGN

3.1 Experimental Design: Prospective, observer blind, multi-site, randomised, controlled, equivalence trial

3.2 Randomisation: Randomisation to either of the two treatment groups (GA or RA) will be by block and stratified by site and gestational age at birth. Gestational age at birth strata will be:

- 26 weeks to 29 weeks and 6 days
- 30 weeks to 36 weeks and 6 days
- 37 weeks and more

Access to randomisation numbers will be via a 24 hour web-based randomisation service set up and maintained by A/[name] at The Data Management & Analysis Centre, Department of Public Health, University of Adelaide, South Australia: http://www.dmac.adelaide.edu.au/gasRandomisation

Entry to the website is password protected.

3.3 Blinding: The anaesthetist will be aware of the group allocation. The psychologist and paediatrician performing the 2 and 5 year neurodevelopmental assessments will be blinded to study group. Parents will not be told which group their child was in but they will be allowed to discover the group and will be told if asked. Parents will be clearly instructed that if they do discover the group then they should not inform the assessing psychologist. A record will be made of whether or not the parents or the psychologist became aware of the allocation. The apnoea assessment and recovery assessment will not be blinded.

3.4 Study duration: The duration of subject participation is five years.

- Children will be enrolled before surgery.
- Data will be collected before and during anaesthesia and in the early postoperative period.
- Formal neurodevelopmental assessment will occur at 2 and 5 years corrected age (see appendix 1 for definition of corrected age).

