4. SELECTION OF SUBJECTS

4.1 Number of subjects: 660

4.2 Inclusion criteria: Any child scheduled for unilateral or bilateral inguinal hernia repair (with or without circumcision).

4.3 Exclusion criteria:

- Any child older than 60 weeks postmenstrual age
- Any child born at less than 26 weeks gestation
- Any contraindication to general *or* spinal/caudal anaesthesia (for example: neuromuscular disorder or coagulopathy)
- Pre-operative ventilation immediately prior to surgery
- Congenital heart disease that has required surgery or will require surgery or which requires ongoing pharmacotherapy
- Known chromosomal abnormality or any other known acquired or congenital abnormalities (apart from prematurity) which are likely to affect development
- Children where follow-up would be difficult for geographic or social reasons
- Families where the primary language spoken at home is *not* the language in which the WPPSI-III will be given [i.e. English for Australian sites, French for Paris site and English or Spanish for US sites]
- Known neurological injury such as cystic periventricular leukomalacia (PVL), or grade 3 or 4 intra ventricular haemorrhage (IVH) (+/- post haemorrhage ventricular dilatation)
- Previous exposure to volatile anaesthesia or benzodiazepines as a neonate or in the third trimester in utero

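### Randomisation is stratified by site and gestational age, but the stated primary model adjusts for gestational age alone; adding site costs almost nothing and protects precision and the per-protocol comparison

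*Protocol*

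**What the plan says.** Protocol 3.2: allocation "will be by block and stratified by site and gestational age at birth", with three gestational-age strata.

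Protocol 8.1: the primary outcome is analysed per protocol, and "The means will be adjusted for gestational age at birth". No other covariate is named. Equivalence is accepted if the two-sided 95% confidence interval lies within -5 to +5 points.

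Protocol 8.2.1 uses the same adjustment for the Bayley III cognitive score and for the other continuous neurodevelopmental outcomes.

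Protocol 8.3 gives the form of the adjustment: "Adjusting the analysis for gestational age at birth, according to the three categories used in the stratified randomization". It sizes the trial on the gestation-adjusted interval, using the "two one-sided equivalence tests method" with SD 15. The result is 598 infants, raised to 660 for loss to follow-up.

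Protocol 4.3 shows that the test language depends on the site: "English for Australian sites, French for Paris site and English or Spanish for US sites". Appendix III plans 15 sites.

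**The concern.** The protocol carries one of its two stratification factors into the model and drops the other without comment. It names the adjustment for its primary outcome and main secondary outcome, so this is a stated choice and can be commented on as such.

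Two things are at stake. First, blocking within site balances the arms on whatever differs between sites. If site predicts IQ and the model ignores it, the between-site variance stays in the residual and the standard error is overstated. Since the whole interval must fit inside ±5, that costs some power. Country, test language, assessor and social mix could all differ by site, though the protocol does not say by how much they move IQ.

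Second, the within-site balance belongs to the randomised set, whereas the primary analysis is per protocol. Under 5.7, infants with a failed awake regional block receive sevoflurane. If they leave the per-protocol set, they leave one arm only. If the failure rate varies by site, the arms can end up with different site mixes, and a model without site cannot correct for that.

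**Working it through.** **Inputs from the protocol.** Margin 5, SD 15, 598 evaluable infants (299 per arm), "with a one-sided alpha of 0.025, applied to the null hypothesis that the two methods of anaesthesia are not equivalent", "power of 90% under the alternative hypothesis that the true mean difference is one standardised score point" (8.3); 15 sites (Appendix III); regional failure quoted as up to 25% (1.4.4).

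**Assumed.** The share of within-gestation variance lying between sites (ICC), shown over 0 to 0.10; block size 4; exclusion rates by site.

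**Step 1: reproduce 598.** SE = 15 × √(2/299) = 1.227. Half-width = 1.96 × 1.227 = 2.40 points. Power = Φ((5 − 1)/1.227 − 1.96) − Φ(−(5 + 1)/1.227 + 1.96) = 90.2%. With t quantiles, power is 89.97% at 596 and 90.07% at 598, so 598 reproduces exactly on the gestation-only interval.

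**Step 2: effect of adding site, by formula.** If SD 15 includes site variation, the residual SD with site in the model is 15 × √(1 − ICC). The gestation-only interval is then wider by the factor 1/√(1 − ICC).

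| Site ICC (assumed) | Half-width, gestation only | Half-width, plus site | Excess width | Power, gestation only | Power, plus site |
|---|---|---|---|---|---|
| 0 | 2.40 | 2.40 | 0% | 90.2% | 90.2% |
| 0.02 | 2.40 | 2.38 | 1.0% | 90.2% | 90.7% |
| 0.05 | 2.40 | 2.34 | 2.6% | 90.2% | 91.6% |
| 0.10 | 2.40 | 2.28 | 5.4% | 90.2% | 93.0% |

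At ICC 0.10 the excess half-width is 2.405 − 2.281 = 0.12 points, and the power difference is 93.0 − 90.2 = 2.8 percentage points.

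**Step 3: simulation with arms balanced within site.** 6,000 trials per setting, 598 infants, 15 sites × 3 gestation strata, true difference 1:

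- ICC 0: half-width 2.408 without site and 2.410 with it.
- ICC 0.05: 2.405 v 2.349; coverage 95.7% v 95.3%; power 90.7% v 91.5%.
- ICC 0.10: 2.398 v 2.285; coverage 96.0% v 95.1%; power 91.9% v 93.2%.

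The power gain is smaller than in Step 2 because blocking by site already makes the gestation-only estimate more precise than its own standard error shows. At a true difference of 5, false equivalence is 2.1% v 2.3% (ICC 0.05) and 2.1% v 2.4% (ICC 0.10), all below the nominal 2.5%.

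**Step 4: per-protocol exclusions from the regional arm.** Without site in the model, bias = cov(exclusion rate, site mean IQ) / (1 − mean exclusion rate). Take an unfavourable case: 5% excluded in half the sites and 25% in the other half (mean 15%, SD 0.10), with the high-exclusion sites being those ranked highest on IQ. For normally distributed site means, each half averages about 0.80 between-site SDs from the centre.

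- ICC 0.05: site SD = 15 × √0.05 = 3.35; bias = 0.10 × 0.80 × 3.35 / 0.85 = 0.32 points.
- ICC 0.10: site SD = 15 × √0.10 = 4.74; bias = 0.10 × 0.80 × 4.74 / 0.85 = 0.45 points.

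Simulation of this worst case gives about 0.3 to 0.4, and adding site removes it. If instead sites form two clusters exactly one site SD above and below the mean, the formula gives 0.10 × 3.35 / 0.85 = 0.39 and 0.10 × 4.74 / 0.85 = 0.56. Simulated false equivalence at the margin is then 4.7% (ICC 0.05) and 5.2% (ICC 0.10) without site, against 2.5% and 2.6% with it.

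A milder case has mean exclusion 10%, between-site SD 0.05 and still perfect correlation. It gives 0.05 × 3.35 / 0.90 = 0.19 and 0.05 × 4.74 / 0.90 = 0.26.

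**The case against.** A reader might infer that the interval is wider than the design allows and that the trial is underpowered as a result. The protocol does not support this. Section 8.3 sizes the trial on the gestation-adjusted interval, and 598 reproduces. Power would fall short only if SD 15 were a within-site SD (89.6%, 88.6% and 86.8% at ICC 0.02, 0.05 and 0.10), and 8.3 does not say that it is.

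A reader might also see a contradiction with 1.4.2, which states: "This potentially confounding variable makes stratified randomisation and a subsequent stratified analysis essential". But the variable meant there is prematurity, and the plan does adjust for that.

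The effect also rests on a between-site variance that the protocol never gives, and several provisions may limit it. Families whose home language is not the test language are excluded (4.3), examiners are trained and video-reviewed across sites (section 10), and the score is standardised. While arms stay balanced within site the error is conservative, which suits the stated aim of 8.1. All of this stands, and it keeps the point modest.

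On bias, the objection is that failure rates would have to track site mean IQ, for which there is no evidence, and that 5.2.3 restricts awake blocks to anaesthetists with success above 90%. This also stands: the bias is a possibility, not a demonstrated fault. It does mean that the error cannot be called conservative in every case.

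Finally, the analysis plan is not shown and may already include site. That does not alter what the protocol says, and 8.1 and 8.2.1 would still need to agree with it.

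**Conclusion.** The point holds as an inexpensive improvement to a stated model, not as an error that undermines the trial. Site is a stratification factor and is missing from the adjustment in 8.1, 8.2.1 and 8.3 without explanation.

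For an assumed site ICC of 0 to 0.10, the interval is about 0% to 5% wider than necessary and power about 0 to 3 points lower than it could be (nearer 0 to 1 in simulation). The ±5 decision would rarely change on this account, and nothing is lost if sites do not differ.

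The per-protocol argument is the less certain but more consequential part. A bias of about 0.3 to 0.4 points needs both a wide spread of exclusion rates between sites and close alignment of those rates with site mean IQ. Neither is documented, so the figure shows what could happen under unfavourable assumptions and is not an estimate for this trial.

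**What to change.** In 8.1 and 8.2.1, state that the mean difference is adjusted for gestational-age stratum and site, with very small sites pooled within country by a rule fixed before unblinding. Bring the wording of 8.3 into line. If site is left out on purpose, give the reason.

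The cost is a sentence in each section and 15 − 1 = 14 degrees of freedom out of roughly 590. Site is already recorded for randomisation, so no new data are needed, and the sample size does not change.

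This change does not deal with other selection that a per-protocol analysis can introduce; it removes only the part that runs through differences between sites.
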